10.9. Appendix 9: Lund-Mackay CT score

Change in the Lund-Mackay CT score percentage of maxillary sinus volume occupied by disease will be assessed in all participants.

The Lund-Mackay CT score evaluates the patency of each sinus using a 0 to 2 scale (0 = normal; 2 = total opacification) and has a total score range from 0 to 24 (higher scores indicate more opacification) [Lund, 1993; Bhattacharyya, 1999].

Sinus	Right sinus	Left sinus		
Frontal	0-2	0-2		
Anterior ethmoids	0-2	0-2		
Posterior ethmoids	0-2	0-2		
Maxillary	0-2	0-2		
Sphenoid	0-2	0-2		
Ostiomeatal complex	0 or 2	0 or 2		
Total	0-12	0-12		
For the sinuses: 0 = no opacification; 1 = partial opacification; 2 = total opacification.				
For the ostiomeatal complex: 0 = not occluded; 2 = occluded.				
Maximum total score: 24				

10.10. Appendix 10: Country-specific requirements

Country-specific local requirements will be added, as and when applicable.

Japan-specific requirements

Additional Japan-specific requirements will be captured within a separate addendum. The content of the Japan addendum is considered administrative.

China-specific requirements

Urinalysis: Urine dipstick will not be performed in China, all urine sample will instead be sent for central laboratory urinalysis. Investigators should be aware of the time needed for central laboratories to return results, and should perform appropriate local investigations if any urgent result is required.

Exploratory biomarkers: Exploratory biomarkers samples will not be collected from participants in China.

Genetics: Genetic Informed Consent will not be collected from participants in China.

France-specific requirements

Informed Consent: In France, a participant will be eligible for inclusion in this study only if he/she is either affiliated to or a beneficiary of a social security category.

10.11. Appendix 11: Recommended Measures Related to COVID-19 Pandemic

10.11.1. Overall Rationale for this Appendix:

COVID-19 pandemic may impact the conduct of clinical studies. Challenges may arise from quarantines, site closures, travel limitations, interruptions to the supply chain for the study intervention or other considerations if site personnel or study participants become infected with COVID-19. These challenges may lead to difficulties in meeting protocol-specified procedures, including administering or using the study intervention or adhering to protocol-mandated visits and laboratory/diagnostic testing.

This protocol appendix outlines measures that may be applicable for any site impacted by the COVID-19 pandemic. The purpose of the appendix is to provide information on the measures to be taken to protect participants' safety, welfare and rights, and promote data integrity.

10.11.2. Study Procedures During COVID-19 Pandemic

During the special circumstances caused by the current COVID-19 pandemic, you should consider specific public health guidance, the impact of any travel restrictions implemented by local/regional health authorities and local institutions, and individual benefit /risk when making enrolment and treatment decisions for trial participants.

Every effort should be made to adhere to protocol specified assessments for participants on study intervention, including follow-up however when not possible, for the duration of these special circumstances, the following measures may be implemented for enrolled participants.

- Clinical investigators should document in site files and in participant notes/Electronic Health Records as appropriate how restrictions related to COVID-19 led to the changes in study conduct and duration of those changes and indicate which trial participants were impacted and how those trial participants were impacted (as per the current local COVID-19 related regulatory guidance).
- Missing protocol required data/visits due to COVID-19 should be noted in participant notes and recorded as a COVID-19 protocol deviation.

10.11.3. Protocol Defined Procedures/Visits:

• Where applicable country and local regulations and infrastructure for home healthcare allow, home healthcare may take place at a location other than the clinical trial site to perform study assessments, which may include collection of blood and urine samples, measurement of vital signs and weight, and preparation and administration of study drug (at the discretion of the investigator). It is the responsibility of the investigator to inform GSK when this occurs and to document in source notes.

- Remote visits may be performed at the participant's home by qualified study personnel or at a local medical facility, unless the investigator deems that a sitevisit is necessary.
- Additional unscheduled safety assessments such as routine blood sampling may be performed at the discretion of the investigator including in the participant's home, if deemed necessary. Biological samples may be collected at a different location, other than the study site (e.g., at participant's home) by qualified study personnel or at a local medical facility according to standard operating procedures and applicable regulations (see note). Biological samples should not be collected if they cannot be processed in a timely manner or appropriately stored until the intended use.
- If visits to a site/home are not feasible, then the medical evaluation of the participant's CRSwNP may take place by telemedicine which will use secure video conferences, phone calls, and a web portal and/or mobile application as a way of communicating with and monitoring the participant's progress. GSK will be accountable for working with the vendor to ensure the site has the required equipment, training and support for this model and should be notified as soon as possible by the investigator that the service is required.
- The study investigator is responsible for ensuring that the identification, management, and reporting of AEs and SAEs are completed in accordance with the protocol and applicable regulations. AEs are first reported by participants to the investigator/study team or may be identified by the study team during interactions with the participants via telemedicine encounters. In addition, mobile nurses may identify AEs as well and report them to the investigator for evaluation. Additionally, AEs may be identified from lab reports, imaging or ECG reports, and other records. As determined by the investigator, the appropriate medical intervention, therapeutic intervention, and/or support measures are instituted, as necessary.
- The participant should be informed of the plan and any potential risks associated with the virtual medium and sign a revised Informed Consent Form if required. IRB/Ethics committee should be informed and/or approve of this change in approach and the process documented in study files.
- The revised schedule of study activities is provided in the SoA in Section 1.3.

Note: If the investigator wishes to conduct a trial visit at a location that has not been previously assessed by GSK, it is the investigator's responsibility to identify an adequate alternate location and to notify GSK of the alternate location. The investigator should ensure that this alternate location meets ICH GCP requirements, is well-equipped to perform study procedures and covered by an adequate insurance. Furthermore, the investigator should have sufficient oversight to ensure that the staff at the alternate location are trained to perform study procedures. Refer to and follow most recent local guidance and regulations if available or refer to FDA or EMA guidance available at time.

10.11.4. Study Intervention:

• If despite best efforts it is not possible to administer the dose of study intervention as defined in the protocol (see Section 6 Study Intervention and Concomitant Therapy), a maximum dose interval of 28 weeks may be used.

- In-clinic visits are required for administration of the study intervention (Week 0 and Week 26).
- In some cases, trial participants who no longer have access to study intervention or the investigational site may need additional safety monitoring (e.g., on withdrawal of an active investigational treatment).

10.11.5. Data Management/Monitoring:

- If the eDiary was provided to the participant, it may be returned to the site by conventional mail after the end of the relevant data collection period (Visit 17 Exit Visit).
- If on site monitoring is no longer permitted, GSK will consider remote Source Data Verification/Source Document Review (SDV/SDR) where permitted by the clinical site/institution. Remote SDV/SDR will be proposed to study sites to meet a patient and/or critical quality need, e.g., to assess participant safety or to ensure data integrity. In case of remote SDV/SDR, GSK will work with the site to ensure participant privacy.
- eCRF/CRF Final or Interim Sign off Process: The PI is responsible for ensuring that the data within the eCRF casebook and any other data sources utilized during the study for each study participant is complete and consistentwith source documents throughout the study (ICH GCP 4.9.1 4.9.2). The PI may sign/re-sign the eCRF from any computer/location by accessing InForm (or other eDC platform) using his/her unique eCRF log-in credentials. The PI may delegate this activity to another medically qualified and trained sub-investigator and this mustbe documented on the Delegation of Responsibilities (DoR) Log. It is recommended that the PI identifies a sub-investigator as a back-up for eCRF signatures. The sub- investigator must be appropriately trained on the protocol and eCRF requirements (with training documented), and the DoR log updated accordingly.
- Essential Document Sign Off Process: If an investigator is unable to print and sign essential documents such as Protocol /Amendment signature page then Email approval can be accepted by replying to the relevant email that is sent by GSK.

10.11.6. Assessments that can be Conducted Outside Clinical Study Site:

Activities/assessments that may be conducted outside of a clinical study site are indicated in Table 1.

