Optional Genetics sample									Х										Genetics sample can be collected at V2 or at any visit during the Treatment Period. Not applicable for China.
Optional Exploratory Blood Biomarker samples		Х			Х				Х							Х			Must be performed pre-dose at V2 and V9. Not applicable for China. A whole blood sample for transcriptomics (Section 8.6.4.2) is collected at V2 and V16 only.
Collect NP surgery samples – Optional									Х										Wherever possible, the removed tissue from a nasal surgery will be collected and

	Sit 1)a, d						Tı	reatn	nent	Peri	od						Withdraw	/Follow Up	
Procedure	į.							1	Wee	k							EW Visit	Follow-up	N
Flocedule	jing	0	4	8	12	16	20	24	26	28	32	36	40	44	48	52	26 or 52	30/56	Notes
	reeni									Vi	sit (±	7 da	ys)						
	Scr	2a	3a	4 c	5a	6b	7a	8 b	9a	10a	11a	12 ^b	13a	14b	15ª	16a	a, e	b, e	
																			stored. Not applicable for
																			China.
Optional Nasal Biopsy sample																Х			Only in participating countries and sites.

Abbreviations: Ab, antibody; ACQ, asthma control questionnaire; AE, adverse event; ANA, antinuclear antibodies; ANCA, antineutrophil cytoplasmic antibodies; CV, cardiovascular, CRSwNP, chronic rhinosinusitis with nasal polyps; dsDNA, double stranded Deoxyribonucleic acid; ECG, electrocardiogram; eDiary, electronic diary; EW, early withdrawal; INCS, intranasal corticosteroids; NP, nasal polyps; MPO, myeloperoxidase; PGIS, patient global impression of severity; PGIC, patient global impression of change; PI: Principal Investigator; PK, pharmacokinetic; PR3, proteinase 3; SAE, serious adverse event; SF-36, 36 item short form health survey; SNOT-22, 22-item sinonasal outcomes test; SRM, study reference manual; VAS, visual analogue scale; VRS, verbal response scale; WPAI-GH, workers productivity and activity impairment – general health; WOCBP, women of childbearing potential; V, Visit.

- a. In-clinic visit.
- b. Telemedicine visit.
- c. Optional home nursing visit (Week 8; V4 only).
- d. Screening window should be 28 days ± 7 days i.e., maximum of 35 days from Day 1 and minimum of 21 days.

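### Protocol Appendix 11 lets home healthcare give study drug during COVID-19 disruption, yet the same appendix requires both doses to be given in clinic (minor)

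*Protocol*

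**What the plan says.** Protocol 10.11.2 introduces contingency steps for when normal adherence is not possible during the pandemic: "the following measures may be implemented for enrolled participants".

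Protocol 10.11.3 then allows home healthcare at a place other than the trial site. Besides sampling, vital signs and weight, its list includes "preparation and administration of study drug (at the discretion of the investigator". The permission is limited:

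- It applies "Where applicable country and local regulations and infrastructure for home healthcare allow".
- The sponsor must be told: "It is the responsibility of the investigator to inform GSK when this occurs and to document in source notes".
- Participants are to be informed and re-consented if required, and the ethics committee is to be involved.
- A note sets conditions for any location the sponsor has not assessed.

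Protocol 10.11.4, on study intervention, states: "In-clinic visits are required for administration of the study intervention (Week 0 and Week 26". If a dose cannot be given as planned, the relief it offers is a longer interval, at most 28 weeks.

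Two further statements in the appendix defer to the schedule. Section 10.11.3 says "The revised schedule of study activities is provided in the SoA in Section 1.3", and 10.11.6 says "Activities/assessments that may be conducted outside of a clinical study site are indicated in Table 1". Footnote c of that table reads "Optional home nursing visit (Week 8; V4 only".

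**The concern.** An investigator who reads 10.11.3 may reasonably conclude that a home nurse can give the Week 26 injection to a participant who cannot travel. Doing so breaks 10.11.4.

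Two things are at stake. The first is safety. The protocol lists anaphylaxis as a potential risk, and Section 6.4 answers it with dosing and observation in the clinic, on-site staff trained in basic life support, and access to prompt transfer. The 2-hour observation would still apply at home, because Table 1 requires it without naming a place. The in-clinic setting and the life-support cover would not be assured.

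The second is the trial record. COVID-19 changes to conduct must be documented, and SAP 6.1.3 has important deviations identified and categorised before unblinding. A home dose is both permitted and prohibited by the current text, so its classification is unclear.

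**Working it through.** The plan gives no figure on this point, so the check sets the provisions side by side.

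| Provision | Place of dosing |
|---|---|
| 10.11.3 | Home healthcare away from the site may prepare and give drug |
| 10.11.4 | In clinic, both doses, no exception |
| 10.11.3 (closing bullet) and 10.11.6 | Defer to the schedule in Section 1.3, Table 1 |
| Table 1 | Dosing visits V2 and V9 both in-clinic; home nursing at V4 only |
| 6.4 | Dosing and observation described as in the clinic; a second site staff member confirms dose and identity |
| 6.2 | Only authorized site staff may give the drug |

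**Step 1: is there any dose to which the permission could apply without conflict?** The study has two doses, Week 0 and Week 26, and 10.11.4 names both. Doses left for off-site administration: 2 − 2 = 0.

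**Step 2: is 10.11.3 a pandemic exception to a normal-times rule?** No. Section 10.11.4 is itself a pandemic rule. It deals with the case where dosing as planned has proved impossible, and it changes the timing but not the place.

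**Step 3: which sentence is out of line?** The Table 1 visit markers are:

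- In-clinic: V1, V2, V3, V5, V7, V9, V10, V11, V13, V15, V16 = 11
- Telemedicine: V6, V8, V12, V14 = 4
- Optional home nursing: V4 = 1
- Total: 11 + 4 + 1 = 16

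Of the 2 dosing visits, 2 are in-clinic and 0 are off-site. Table 1 also requires an ECG and a physical examination before the Week 26 dose, and 7.1.3 uses that visit's machine-read ECG for the QTc stopping criteria. The home tasks named in 10.11.3 include neither, although the list is not exhaustive. The 10.11.3 wording is therefore the odd one out. These counts show the scope of the conflict, not an amount of harm.

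**Step 4: which rules would a home dose break?** It would break 10.11.4 and depart from 6.4. It would break 6.2 only if the home nurse is not authorized site staff, which the documents do not settle.

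**Step 5: how much room does the existing fallback give?** A 28-week interval allows (28 − 26) × 7 = 14 days beyond nominal Week 26. Table 1 already allows 7 days either side of each visit, so the gain over the ordinary window is 14 − 7 = 7 days.

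**The case against.** The strongest reply is that ordinary reading resolves the conflict. Appendix 11 offers recommended measures, the 10.11.3 words are one item in a general list of what may be done, and 10.11.4 is the dedicated and mandatory section. A permission can be left unused, so no site is forced into a breach. That supports a low severity, but 10.11.3 still allows what 10.11.4 forbids.

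A second reply is that a place other than the trial site could be a local clinic, so off-site and in-clinic are not strict opposites. This narrows the conflict without removing it, because the protocol's Terms table describes home healthcare services as mobile professionals working remotely.

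Third, the safety gap is inferred. Nothing in 10.11.3 waives Section 6.4, and the note on unassessed locations asks for suitable equipment and trained staff. That is fair as partial cover, but the note does not mention life support.

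Fourth, the conflict could be removed the other way, by qualifying 10.11.4 with explicit observation and life-support conditions. That would work on paper, but it would also mean changing Table 1 and reconciling 6.4. The point that the 28-week limit adds only about a week to the normal window stands, and it is a real cost of keeping dosing in clinic.

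**Conclusion.** The concern holds. Two current provisions of one appendix contradict each other on where study drug may be given, and Table 1 and Section 6.4 show that the home-dosing words in 10.11.3 are the ones to change.

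Severity is minor. The exposure is realistically one of two doses, Week 26, and only in COVID-19 circumstances. Limiting it to Week 26 assumes that the measures for enrolled participants do not reach the first dose; the protocol does not define the term. How often a site would use the permission cannot be estimated from the documents. No endpoint, estimand, alpha level, sample size or primary analysis changes.

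**What to change.** In Protocol 10.11.3, delete only the words on preparing and giving study drug. Keep blood and urine sampling, vital signs and weight as home tasks at the investigator's discretion. Add one sentence: *Study intervention is administered in clinic only (see 10.11.4).*

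The cost is one deleted phrase and one cross-reference. No new procedure is needed, because 10.11.4 already supplies the longer interval for a participant who cannot attend at Week 26.

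The downside is that a participant who cannot reach a clinic within 28 weeks may miss the second dose, unless a longer delay is agreed with the Medical Monitor under 5.6 and 7.1.4. The protocol does not say whether the 28-week limit overrides those sections. Such a participant can still complete the study under 4.4.

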10.12. Appendix 12: Protocol Amendment History

Amendment 4 (12 March 2024)

Overall rationale for the current Amendment: The protocol has been amended primarily to change the pooled analysis endpoint of time to first nasal surgery (actual) from 'Other' to 'Secondary' to address feedback from the FDA. Additional participant analysis sets have been added and updates to existing analysis sets have been made to exclude data from sites managed by Medipharma, a Japanese Site Management

Organisation, in response to the Japan Ministry of Health, Labour and Welfare (MHLW) confirming GCP violations in several studies involving Medipharma. Other changes to the protocol reflect updates to the GSK protocol template.

LIST OF MAIN CHANGES IN THE PROTOCOL AND THEIR RATIONALE:

Section # and title	Description of change	Brief rationale
Abbreviations	Addition of abbreviations	Added abbreviations introduced in this
Abbieviations	Addition of abbreviations	protocol amendment.
Terms	Addition of terms	For clarification of terms used in the
101113	Addition of terms	protocol.
Section 1.1 Synopsis,	Changed the pooled analysis	Based on regulatory authority feedback.
Section 3.2 Objectives and	endpoint of 'time to first	Bassa sirregulatory additionly resultation
Endpoints for Pre-specified	nasal surgery (actual)' from	
Pooled Analysis Across	'Other' to 'Secondary'.	
Studies 217095 (This	Carlor to Cocorradity :	
Study) and 218079		
(Replicate Study)		
Section 1.1 Synopsis,	Added 'for CRSwNP' for the	For clarification of endpoint assessment.
Section 3.2 Objectives and	endpoint related to systemic	
Endpoints for Pre-specified	corticosteroids.	
Pooled Analysis Across		
Studies 217095 (This		
Study) and 218079		
(Replicate Study)		
Section 1.1 Synopsis,	Added 'up to Week 52' for	For clarification of endpoint assessment.
Section 3.2 Objectives and	the endpoint related to need	·
Endpoints for Pre-specified	for surgery.	
Pooled Analysis Across		
Studies 217095 (This		
Study) and 218079		
(Replicate Study)		
Section 2.2.1.1	Reference to the	To update to the current effective IB
Depemokimab	Investigator's Brochure has	version 5.0.
(GSK3511294) Long-Acting	been updated to the latest	
IL-5 and Section 2.3	effective version of the IB.	
Benefit/Risk Assessment		
Section 3.5 Secondary	Addition of estimand	To provide the estimand definition for
Estimands for	definition for the pooled	this endpoint, which is now a pooled
Pre-specified Pooled	secondary endpoint of 'Time	analysis secondary endpoint.
Analysis Across Studies	to first nasal surgery	
217095 (This study) and	(actual)'.	
218079		
Section 6.1 Study	Updated to indicate	Updated for clarity and to reflect
Intervention(s)	'Depemokimab' as IMP	changes made to the GSK protocol
Administered	instead of 'Experimental' and	template.
Table 3	that Non-IMP and authorized	
	AxMP/unauthorized AxMP	
0	are Not Applicable.	Edited at a succession
Section 6.8.2 Prohibited	Corrected the washout	Editorial correction.
Medications	period prior to Screening	

Section # and title	Description of change	Brief rationale
Table 4	visit for non-biologic and biologic investigational products; corrected the dupilumab trade name.	
Section 7.2 Participant Discontinuation/Withdrawal from the Study	Updated terminology: replaced 'study discontinuation' with 'study withdrawal'.	To provide clarity and consistency in terminology between "discontinuing treatment" and "withdrawal from study" and to reflect changes made to the GSK protocol template.
Section 7.3 Lost to Follow Up	Updated to clarify that other contact methods can be used along with telephone calls for follow up.	For clarification and to reflect changes made to the GSK protocol template.
Section 8.4.9 Medical Device Deficiencies	Updated to clarify that if the sites use non-sponsor medical devices, then the investigators are obligated to report any device deficiencies to the legal manufacturer of the devices directly.	For clarification and to reflect changes made to the GSK protocol template.
Section 9.1.1 Multiplicity Adjustment and Figure 4	This section and the figure were updated to reflect the addition of time to first nasal surgery (actual) as a secondary endpoint for the pooled analysis. Updates to indicate that the time to first nasal surgery (actual) will only be tested if statistical significance is achieved for time to first nasal surgery (actual or entry on waiting list). Updated the number of secondary endpoints to 4.	To align with changes to the statistical hierarchy.
Section 9.2 Analysis Sets	Update to the Full Analysis Set (FAS) to exclude participants from sites managed by Medipharma, and addition of modified analysis sets including these participants. Added additional participant analysis sets for PK and specific analysis sets for China and Japan.	Updated to align with the Statistical analysis plan in response to the Japan Ministry of Health, Labour and Welfare (MHLW) confirming GCP violations in several studies involving Medipharma and to describe analysis sets required for PK analyses and submissions in China and Japan.
Section 9.3.1 Co-primary and Key Secondary Endpoint(s) Analyses	Added the time to first nasal surgery (actual) endpoint under secondary pooled analyses and detailed the pooled analysis description.	Updated to align with updates in other sections of the protocol and Statistical analysis plan.

Section # and title	Description of change	Brief rationale
Section 10.1.5 Data	Added a statement related to	To comply with requirements to protect
Protection	GSK internal policy for	personal data and to reflect changes
	reporting data incidents or	made to the GSK protocol template.
	breaches.	·
Section 10.1.7	Updated plain language	Updated to align with GSK's disclosure
Dissemination of Clinical	terminology to layperson	requirement and regulatory disclosure
Study Data	summary of results.	requirement and to reflect changes
	 Added a statement that 	made to the GSK protocol template.
	where required by	
	regulation, the names of	
	the sponsor signatory	
	and investigator	
	signatory will be made	
	public.	
	Deleted the wording	
	related to SHARE	
	initiative.	
	 Added a statement 	
	related to data sharing	
	and protecting PI.	
Section 10.1.11 Publication	Updated wording around	Updated to align with the new policy on
Policy	GSK seeking to publish	Ethical Scientific Research and to reflect
	medically or scientifically	changes made to the GSK protocol
	significant results in peer-	template.
	reviewed scientific literature.	
Section 10.3.5 Reporting of	Additional instruction to the	Updated for clarification and to reflect
SAE to GSK; Section 10.7.4	site to report to the	changes made to the GSK protocol
Recording and Follow-Up	concerned Competent	template.
of AE and/or SAE and	Authority via the national	
Device Deficiencies;	spontaneous reporting	
Section 10.7.5 Reporting of SAEs	system if they become aware of any serious,	
SAES	nonserious AEs, pregnancy	
	exposure, related to any	
	GSK product/device that is	
	not part of the study design.	
Section 11 References	Deleted references (Bretz	Correction as these references were not
	2009, Wang 2003) which	cited.
	were not cited in the protocol	
All sections	Other minor editorial changes to improve readability.	

Amendment 3 (18 October 2023)

This amendment is considered to be substantial based on the criteria set forth in Article 10(a) of Directive 2001/20/EC of the European Parliament and the Council of the European Union.

Overall Rationale for the Amendment:

- To reduce the number of participants required to provide PK samples at Week 52 (Visit 16/EW Visit) to approximately 200.
- To add an optional nasal biopsy sample collection at Week 52 (Visit 16).
- To update the statistical testing hierarchy.
- To move the asthma-related endpoints to the pooled analyses.
- To amend the definition of the nasal surgery endpoint included in the pooled analysis statistical hierarchy from 'actual' to 'required'.
- Other changes include clarification on NP Scoring guidance and updates to language related to regulatory, ethical, and study oversight considerations.

List of Main Changes in the Protocol and Their Rationale:

Section # and title	Description of Change	Brief Rationale
Terms	Addition of terms and definitions.	For clarification of terms used in the protocol.
Section 1.1. Synopsis, Section 3.1. Objectives and Endpoints, Section 3.2. Objectives and Endpoints for Pre-specified Pooled Analysis Across Studies 217095 (This Study) and 218079 (Replicate Study), Section 3.4. Secondary Estimands, Section 3.5. Secondary Estimands for Pre-specified Pooled Analysis Across Studies 217095 (This Study) and 218079	To move the asthma-related endpoints (ACQ-5 Score and exacerbations) to the pooled analyses. To amend the definition of the nasal surgery objective and endpoint included in the pooled analysis statistical hierarchy from 'actual' to 'required'. To update the definition of the 'Other' objective and endpoint for nasal surgery to count actual surgery only.	To ensure sufficient power for the asthma-related endpoint analyses. To account for (1) the fact that there may be some delay between the requirement for surgery and actually having a surgery, during which time participants will be on a waiting list and (2) country-level variations in medical practices including potential for extended waiting list durations.
Section 1.3. Schedule of Activities (SoA)	PK samples at Week 52 (Visit 16/EW Visit) will be collected for approximately 200 participants rather than all participants. Optional nasal biopsy sample collection added at Week 52.	Samples from approximately 200 participants at Visit 16 are sufficient for PK analysis. To better understand the biological responses to depemokimab within the tissue and the relationship to clinical responses.
Section 2.3.1. Risk Assessment, Section 10.3.5. Reporting of SAE to GSK, Section 10.7.5. Reporting of SAEs	Deleted reference to the SAE Coordinator.	The SAE Coordinator role no longer exists.

Section # and title	Description of Change	Brief Rationale
Section 3.5. Secondary	Addition of secondary estimand	To align with changes to the
Estimands for Pre-specified	information for the ACQ-5 Score	statistical hierarchy.
Pooled Analysis Across	endpoint.	,
Studies 217095 (This Study)	·	
and 218079		
Section 4.4. End of Study	Updates to the definition of study	For clarification and alignment
Definition	completion.	across the clinical development
		program.
Section 5.1. Inclusion	Replaced reference to	To clarify the endoscopic NP
Criteria	"Appendix 10" with "Clario Video	scoring guidance used by sites and
	Guideline".	central reader.
Section 5.3. Randomization	Updated Randomization	To clarify what medications are
Criteria	Criteria 9 on maintenance	permitted during the run-in period.
	therapy to prohibit new use of	
	systemic corticosteroids during	
	the run-in period.	
Section 6.8.1. Permitted	Added clarifications on the use of	To clarify what medications are
CRSwNP and Asthma	short courses of systemic	permitted during the study.
Medications	corticosteroids, antibiotics, and	
	saline nasal douches during the	
0 11 70 8 11 1	study.	T 1 11 B1
Section 7.2. Participant	Participants who are prematurely	To clarify eDiary requirements for
Discontinuation/Withdrawal	withdrawn from study should be	participants who are withdrawn
from the Study	encouraged to complete their	from study.
Castian O Chada	eDiary up until their EW Visit.	ND seems do not noce a viel, of
Section 8. Study Assessments and	Removed requirement for NP	NP scores do not pose a risk of
	scores to be blinded to study and site staff.	unblinding the participant's
Procedures		intervention assignment. To clarify the endoscopic NP
Section 8.2.1. Endoscopic NP Score	Replaced reference to "Vendor manual" with "Clario Video	scoring guidance used by sites and
NF Score	Guideline".	central reader.
Section 8.5	PK samples at Week 52	Samples from approximately
Pharmacokinetics	(Visit 16/EW Visit) will be	200 participants at Visit 16 are
T Harmacokinetios	collected for approximately	sufficient for PK analysis.
	200 participants rather than all	- Camarant for the analysis
	participants.	
Section 8.6.4.3.2. Nasal	Optional nasal biopsy sample	To better understand the biological
Biopsy	collection added at Week 52.	responses to depemokimab within
· ·		the tissue and the relationship to
		clinical responses.
Section 9.1.1. Multiplicity	Text and Figure 4 updated:	To align with changes to the
Adjustment	ACQ-5 Score endpoint moved to	statistical hierarchy.
	the pooled analysis statistical	
	hierarchy and definition of the	
	nasal surgery secondary	
	endpoint in the pooled analysis	
	hierarchy updated to include	
	entry on waiting list.	
Section 9.2. Analysis Sets	The "modified Intent-to-treat"	To align on analysis set naming
	population has been renamed as	across the clinical development
	the "Full Analysis Set".	program.

Section # and title	Description of Change	Brief Rationale
Section 9.5. Sample Size Determination	Updates to assumptions and power to reflect inclusion of entry on waiting list as an event for the nasal surgery secondary endpoint.	To align with the updated definition of the nasal surgery secondary endpoint included in the statistical hierarchy.
Section 10.1.5. Data Protection	Added a statement related to protection of the personal data of the investigator and site staff.	To comply with requirements to protect personal data.
Section 10.1.7. Dissemination of Clinical Study Data	Added timing for disclosure of clinical study data.	To align with sponsor policies on the dissemination of clinical study data.
Section 10.1.8. Data Quality Assurance	Added a statement related to external sharing of source documents for review and storage.	To state how long documents will be stored by the external body.
Previous Section 10.10 Appendix 10: Endoscopic NP Score	Deleted Appendix 10 (nasal polyps scoring).	Now referencing 'Clario Video Guideline' to clarify the endoscopic NP scoring guidance used by sites and central reader.
Throughout	Minor editorial and document formatting revisions.	Minor, therefore, have not been summarized.

Amendment 2 (26 October 2022)

This amendment is considered to be substantial based on the criteria set forth in Article 10(a) of Directive 2001/20/EC of the European Parliament and the Council of the European Union.

Overall Rationale for the Amendment:

This protocol was modified following release of a protocol clarification letter in April 2022. All details included in the protocol clarification letter are now incorporated into the study protocol. Protocol changes are described in the table below.

Section	Description of Change	Brief Rationale
Section 1.3 Schedule of Activities	Updated notes for Medical history; Past and current medical conditions' Physical exam 12-lead ECG Assessment of endoscopic NP score CT Scan eDiary Compliance Check Parasitic Screening	Modified to align with the corresponding amendments made in rest of the protocol.

Section	Description of Change	Brief Rationale
	 Urinalysis Pregnancy test (WOCBP only) Footnote Deleted row on Optional Nasal filter samples for biomarkers 	
Section 1.3 Schedule of Activities	Physical examination to be performed prior to dosing at Visit 9 as well	Correction/Clarification
Section 1.3 Schedule of Activities	Updated footnote to provide information on urinalysis in China	To comply with local policy
Section 5.1 Inclusion Criteria	Updated definition of severe NP symptoms	Clarification
Section 5.2. Exclusion Criteria	Exclusion criteria 24 on prior/concurrent clinical study experience updated to include washout period for non-biologics besides biologics, by adding a reference to Section 6.8.2	Clarification
Section 6.8 Concomitant Therapy	Modified heading to "Prior and Concomitant therapy"	Correction
Section 6.8.2 Table 4	Table 4 Prohibited medicated updated to include more clarity on 'time period prior to screening visit' for non-biologic and biologic products	Correction/ Clarification
Section 6.8.3. COVID-19 Vaccines and treatments	Updated information on the permitted COVID-19 treatment	Clarification
Section 7.1.3.QTc Stopping Criteria	Added the definition for baseline QTcF value and the procedure to assess QTc stopping criteria after randomization and at Visit 9 (Week 26)	Clarification
Section 8.2.1. Endoscopic NP Score	Updated window period for nasal endoscopic assessment	Correction
Section 8.2.2.2. Overall Visual Analogue Scale (VAS) Symptoms Score	Update regarding final VAS scores assessment/interpretation	Correction/ Clarification

Section	Description of Change	Brief Rationale
Section 8.2.3. Computed Tomography (CT) Scan	Text modified to clarify that CT scan must be performed prior to randomization and should be the last assessment performed, where possible. Protocol updated to outline minimum criteria that need to be verified prior to the first CT scan, if it cannot be performed as the last assessment before randomization, in line with a protocol clarification letter released in April 2022.	Correction/ Clarification
Section 8.6.4.3. Surgical Samples	Section on Nasal Filter Samples removed	Correction
Section 9.1. Statistical Hypotheses	Replaced the statistical term superiority with inequality	Clarification
Section 10.1.4. Recruitment Strategy	New section added on recruitment strategy employed for the study	To comply with EU CTR
Section 10.1.5. Data Protection	More information added on data protection as per the new protocol template	To comply with EU CTR
Section 10.1.10. Study and site start and closure	Added a new appendix section 10.1.10 on Study and Site start and closure as per new protocol template (effective 29 June 2022)	To comply with EU CTR
Section 10.2. Appendix 2: Clinical Laboratory Tests	Appendix Table 1 updated with the visit days for pregnancy testing, and the parasitic screening tests (stool microscopy for ova and parasites) for central laboratory testing.	Clarification
Section 10.11. Appendix 11: Country-specific requirements	Updated that urine samples from China will be sent for central laboratory urinalysis	Clarification
All sections	Other minor, grammatical, or typographical corrections made to improve readability.	

Amendment 1 (09 February 2022)

This amendment is considered to be substantial based on the criteria set forth in Article 10(a) of Directive 2001/20/EC of the European Parliament and the Council of the European Union.

Overall Rationale for the Amendment:

